Subjects in Group B2 who tolerated and effectively mobilized with plerixafor were given the option to postpone drug product manufacture until Group C opened, to allow drug product manufacture using plerixafor mobilized cells. In Group C, subjects for whom adequate HSCs are collected to achieve the minimum cell dose but not for rescue, and who do not tolerate plerixafor or do not effectively mobilize with plerixafor may be offered the option of bone marrow harvest for collection of back-up cells only, provided that drug product manufactured from mobilized cells has met criteria for dispositioning for clinical use.

As of Version 8.0 of this protocol, Group C will include adolescent subjects ≥ 12 and < 18 years of age in addition to subjects ≥ 18 and ≤ 50 years of age. It should also be noted that while all Group A subjects and some Group B subjects received drug product manufactured using “Process 1”, all current and future Group C subjects will receive drug product manufactured using an optimized process termed “Process 2”. Treatment with drug product manufactured using Process 2 (versus Process 1) has resulted in increased drug product VCN, peripheral blood VCN, and HbA^{T87Q} levels across multiple bluebird bio-sponsored clinical studies.

The drug product must be release tested and dispositioned for clinical use and stored at the study site before the subject can begin myeloablative conditioning with busulfan.

Stage 3 –Myeloablative conditioning and infusion of bb1111

The subject’s suitability for transplant will be reconfirmed with clinical laboratory tests (complete blood count [CBC], serum chemistry, liver function tests, and pregnancy test), physical examination, performance status, cytogenetics, and other tests based on institutional requirements. The results of these tests will be reviewed, and availability of the drug product on site and the availability of back-up cells will be confirmed before the site can proceed with conditioning.

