5.2.5. Conditioning

5.2.5.1. Busulfan Dosing

Myeloablative conditioning of the subject will be performed using busulfan. Conditioning will only begin after the following criteria are met:

- all drug product lots to be used for the subject have been release tested, dispositioned for clinical use, and stored at the clinical site
- a sufficient number of back-up cells has been collected and stored at the clinical site
- the subject has undergone interim assessments for updated medical history, AE, concomitant medications, physical examination, vital signs, and laboratory tests, all as per the SOE, and continues to meet the eligibility criteria based on these results
- subjects have undergone a transfusion regimen ($Hb > 10 \text{ g/dL}$ and $HbS < 30\%$) and are off HU for at least 2 days and iron chelation for at least 7 days prior to the start of conditioning
- results of conventional cytogenetics (karyotyping) and cytogenetics by FISH from the bone marrow have been received and reviewed by the Investigator and the Medical Monitor; in the presence of a chromosomal abnormality or genetic mutation that does not render the subject ineligible for HSCT per the Investigator's judgment, approval of the Medical Monitor is required before the subject can proceed with conditioning

(see [Section 6.2.11](#)) and subject must sign appropriate informed consent before proceeding with conditioning and treatment with bb1111.

Busulfan will be administered at a starting dose of 3.2 mg/kg/day for 4 consecutive days via IV infusion on Days -6 through -3. The preferred schedule is busulfan via a central venous line (CVL) as a 3-hour infusion once daily for 4 consecutive days for a total of 4 doses. Divided dosing is permitted. In this case, busulfan should be administered as a 2-hour infusion every 6 hours for 16 consecutive doses. For subjects weighing < 35 kg, a q6h dose of 0.8 mg/kg is preferred; for subjects weighing \geq 35 kg, either once daily (qd) or q6h dosing can be used, at the discretion of the Investigator. Please note that the timing of busulfan PK sample collection is based on whether a 2-hour or 3-hour infusion is used.

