Clinical sites that use a test dose of busulfan before myeloablation to pre-determine the busulfan pharmacokinetics and predict an optimal dose may do so in this protocol. The recommended test dose of busulfan is 0.8 mg/kg, administered approximately 3 to 10 days before planned initiation of conditioning. Note that clinical sites must be able to measure first and third day busulfan PK, as described below.

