³⁰Baseline assessment should occur as close to Day -90 as possible, and where possible, must occur before start of pRBC transfusions. Subjects should complete PRO questionnaires at the beginning of the Visit (prior to undergoing any other procedures during the Visit.

Table 3: Schedule of Events: Conditioning and Drug Product Infusion

	Preconditioning Up to 7 days before busulfan	Conditioning Day -6 to -3 inclusive	Infusion Day 1	Day 2 until hospitalization discharge
Physical examination ^a	X	X	X ^b	X ^b
Performance status ^c	X			
Vital Signs ^d	X	X	X ^e	X ^f
Local lab: Blood for clinical laboratory tests				
Hematology ^g	X	X	X	X ^h
Serum Chemistry ⁱ	X	X	X	X
Coagulation Analysis ^j	X			
Iron Metabolism Studies ^k	X			
Haptoglobin	X			
Local lab: Blood for serology	X ^l			
Local lab: Blood for serum β -human chorionic gonadotropin for women of child-bearing potential (serum pregnancy test)	X			
Local lab: Blood for electrophoresis to assess globin fractions (i.e., %HbS, %HbA, %HbF)	X ^m			X ⁿ
Bone marrow aspiration ^o :				
Bone marrow smear ^p	X ^q			
Local lab: Bone marrow for conventional cytogenetics (karyotyping)	X ^q			
Central lab: Bone marrow for storage ^r	X ^q			
Central lab: Blood for next generation sequencing (NGS) mutational testing ^s	X ^q			
Central lab: Blood for storage ^r	X ^q			
Sperm / testicular tissue or oocyte banking, if requested	X			
Reconfirmation of suitability for transplant	X ^t			
Anti-seizure prophylaxis	X ^u	X ^u		
Busulfan chemotherapy (daily or q6h regimen, for 4 days)		X		
Local lab: Blood for busulfan pharmacokinetics ^v	X	X		
Infusion of bb1111			X	
Transfusion regimen	X ^w			

Table 3: Schedule of Events: Conditioning and Drug Product Infusion

	Preconditioning Up to 7 days before busulfan	Conditioning Day -6 to -3 inclusive	Infusion Day 1	Day 2 until hospitalization discharge
Vaso-occlusive event collection		Continuous from ICF signing		
Adverse event collection		Continuous from ICF signing		
Concomitant medication collection ^x		Continuous from ICF signing		

^a Any leg (skin) ulceration noted upon physical exam or as part of medical history must include severity classification.

^b To be performed on Day 1 before drug product infusion. A physical examination should be performed at least twice a week until discharge.

^c Karnofsky performance status (\geq 16 years of age) or a Lansky performance status ($<$ 16 years of age).

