^t Review CBC, serum chemistry (chemistry will include sodium, potassium, chloride, bicarbonate, blood urea nitrogen, creatinine, calcium, phosphate, albumin, total protein, uric acid, LDH, liver enzymes [GGT, ALP, ALT, AST, direct and total bilirubin], glucose and CRP), physical examination, cytogenetics, and performance status; verification that the drug product has been dispositioned for clinical use, is available on site and that back-up cells are available. If PFTs have not been performed within 3 months of initiation of conditioning, then these tests must be repeated prior to conditioning. While not mandatory, cardiac Doppler echocardiology (including left ventricular ejection fraction) and cerebral MRI should be repeated prior to conditioning if clinically indicated.

- ^u Anti-seizure prophylaxis to start at least 12 hours before initiating busulfan and to continue at least 24 hours after completion of 4-day busulfan course.
- ^v Blood for busulfan PK collected at Preconditioning time point only if a busulfan test dose was administered. Clinical sites must be able to measure first and third day busulfan PK. Based on busulfan PK results for day 1 and day 3 of busulfan dosing, busulfan dose adjustments should be made for subsequent dosing. If feasible, daily busulfan PK measurement is recommended. In addition, busulfan levels will be measured 48 and 72 hours after final dose of busulfan for retrospective confirmation of adequate wash-out.
- ^w Transfusion regimen should be initiated at least 60 days prior to stem cell harvest and continue through to start of conditioning. Last exchange transfusion must occur within 1 week of start of conditioning.
- ^x Hydroxyurea must be discontinued at least 30 days before stem cell harvest and at least 2 days before initiating busulfan. Iron chelation must be discontinued at least 7 days prior to stem cell harvest and 7 days before initiating busulfan.

Table 4: Schedule of Events: Follow-up

Procedures	Follow-Up: Day (D), Month (M) (Visit Window, days)										
	D30	D60	D90	D135	D180	D270	D360	D450	D540	D630	D720
	M1 (±7)	M2 (±7)	M3 (±7)	M4.5 (±14)	M6 (±14)	M9 (±14)	M12 (±30)	M15 (±30)	M18 (±30)	M21 (±30)	M24 (±30)
Physical Examination ¹	X	X	X	X	X	X	X	X	X	X	X
Chronic pain assessment ²					X		X		X		X
Performance Status ³					X		X		X		X
Tanner staging (for subjects < 18 years of age)					X		X		X		X
Vital signs ⁴	X	X	X	X	X	X	X	X	X	X	X
Local lab: Blood for clinical laboratory tests ⁵											

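### No text ties a current pregnancy test to the optional busulfan test dose, which may come before the only pregnancy test scheduled after the last harvest

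*Protocol*

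**What the plan says.** **Test dose.** Protocol Section 5.2.5.1 permits sites that use a busulfan test dose to give one in this study: "The recommended test dose of busulfan is 0.8 mg/kg, administered approximately 3 to 10 days before planned initiation of conditioning". No condition of any kind is attached to it.

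**Scheduled pregnancy tests.** Women of child-bearing potential have a serum test at Screening and again up to 7 days before harvest (Table 2). There is one more in Table 3, in the column headed "Preconditioning Up to 7 days before busulfan". Table 4 has none. Section 5.5 adds a repeat rule, but it concerns readiness for mobilization.

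**What must precede conditioning.** Section 3.1 (Stage 3) reconfirms suitability for transplant with tests that include "serum chemistry, liver function tests, and pregnancy test". The results are reviewed, and availability of drug product and back-up cells "will be confirmed before the site can proceed with conditioning". The list in Section 5.2.5.1, which calls for laboratory tests per the schedule and continuing eligibility, opens with "Conditioning will only begin after the following criteria are met". Section 6.2.11, on the same reconfirmation, does not name a pregnancy test.

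**Hazard and other controls.** Section 6.2.31 describes busulfan as teratogenic in animals. Exclusion criterion 21 bars pregnancy and requires contraception from consent, and Section 6.2.31 requires a highly effective method from Screening. Section 6.1 allows scheduled procedures to be done at unscheduled visits.

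**The concern.** A test dose is the first exposure to busulfan, yet the pregnancy test nearest to it is placed by reference to the later conditioning course. A site that follows the text exactly could give the test dose on the strength of a pregnancy test done before harvest, several weeks earlier. At stake is avoidable fetal exposure to a drug that the protocol itself flags as teratogenic in animals. No endpoint or analysis of the trial is affected. This is a patient-safety point about the schedule.

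**Working it through.** **1. What busulfan means in the Table 3 column header.** Two footnotes to the same table settle it.

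- Footnote v: "Blood for busulfan PK collected at Preconditioning time point only if a busulfan test dose was administered". A sample taken after a test dose cannot be drawn in a window that closes before that dose, so the header's busulfan is the later course.
- Footnote x: "Hydroxyurea must be discontinued at least 30 days before stem cell harvest and at least 2 days before initiating busulfan". Section 5.2.5.1 states the same rule for entry to conditioning, namely that subjects "are off HU for at least 2 days and iron chelation for at least 7 days prior to the start of conditioning". Table 3 therefore uses initiating busulfan and starting conditioning for the same moment.

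**2. Where the test dose falls.** Conditioning starts on Day -6 (Section 5.2.5.1).

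- The column opens 7 days earlier, on Day -13.
- A test dose 3 to 10 days before conditioning falls on Day -9 to Day -16.
- At 8, 9 or 10 days before (Days -14 to -16), the dose is 1 to 3 days ahead of the column. That is 3 of the 8 whole-day options.
- At 3 to 7 days before (the other 5 options), dose and pregnancy test share the window, and no sentence orders them.

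**3. Age of the last test sure to precede the dose.** Inputs: about 2 months from mobilization to infusion (Section 5.5), taken as 2 × 30.4375 = 60.9, or 61 days; one mobilization cycle; a pre-harvest test 0 to 7 days before mobilization (Table 2); and 6 or 7 days from Day -6 to Day 1, depending on whether a Day 0 is counted.

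| Test dose, days before conditioning | Days before infusion | Days after mobilization | Age of last test (add 0 to 7) |
|---|---|---|---|
| 8 to 10 | 8+6=14 to 10+7=17 | 61-17=44 to 61-14=47 | 44 to 54 days |
| 3 to 7 (pregnancy test done after the dose) | 3+6=9 to 7+7=14 | 61-14=47 to 61-9=52 | 47 to 59 days |

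Taken together this is 44 to 59 days: 44/7 = 6.3 to 59/7 = 8.4 weeks.

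**4. Sensitivity to the interval.** The documents give only the approximate 2 months; the other two intervals are assumptions to show the range over all test-dose days from 3 to 10.

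- 1.5 months (46 days): 46-17 = 29 to 46-9+7 = 44 days.
- 3 months (91 days): 91-17 = 74 to 91-9+7 = 89 days.
- Second mobilization cycle at least 14 days later (Section 5.2.3), with its own pre-harvest test and the same infusion date as in the 2-month case: at most 59-14 = 45 days.
- Back-up marrow harvest: allowed only once drug product has met its disposition criteria (Sections 5.2.2 and 5.2.3), so it falls late, and Table 2's pre-harvest column covers it. Those women would have a more recent test.

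**5. Dose and reach.** The test dose is 0.8/(4 × 3.2) = 0.8/12.8 = 6.25% of the starting course. SAP Table 1 records 36 Group C infusions against about 41 planned (Protocol Section 4.1), so about 41-36 = 5 subjects of either sex remain.

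**The case against.** **A test dose is busulfan, so the header already covers it.** This is the best textual reply, because the header does not say conditioning. It fails against footnotes v and x. Even if it were accepted, a single test done up to 7 days before a dose given 10 days before conditioning could be 10+7 = 17 days old when conditioning starts, so one scheduled test could not be within 7 days of both exposures. Section 3.1 should not be added as evidence on the header: it states what must precede conditioning and does not define the column.

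**Pregnancy tests are required before the test dose.** True, and a reader might wrongly infer that none is. The Screening and pre-harvest tests both come first. The gap is that no current test is tied to the dose.

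**Other controls apply throughout.** Contraception, the pregnancy exclusion, institutional testing and unscheduled visits all lower the risk, and that stands. But the protocol schedules three pregnancy tests on top of contraception, so it does not treat contraception as enough, and nothing requires the unscheduled test.

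**Section 4.5 proves intent.** A reader might take its listing of pregnancy before conditioning as a withdrawal ground to mean that the plan aims to detect pregnancy before any busulfan. It does not go that far: its reference point is conditioning.

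**Reach may be nil.** This also stands. The test dose is optional and depends on site practice, and SAP Section 5.2 is written for the final study report. The documents do not say that dosing has ended, and they do not show that any woman is now exposed to this gap.

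**Conclusion.** The gap is real in the text and narrow in effect. A busulfan test dose is allowed with no current pregnancy test tied to it: at 8 to 10 days before conditioning it precedes the Table 3 column, and at 3 to 7 days the order is left open. The last assured test is the one before the most recent harvest. The figure of roughly 6 to 8 weeks holds only for a 2-month interval and a single harvest; it should not be read as the usual age of the test. It affects only women of child-bearing potential not yet conditioned, at sites that use a test dose: at most a few, and possibly none. It is worth correcting as a cheap safety improvement, and worth correcting before the text is reused even if nobody remains to be dosed.

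**What to change.** In Section 5.2.5.1, after the test-dose sentence, and in Table 3 footnote v, add: women of child-bearing potential must have a negative serum pregnancy test within 7 days before any busulfan, including a test dose.

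Keep the existing test within 7 days before conditioning. One test may serve both purposes if it meets both limits, which is possible when the test dose is given 3 to 7 days before conditioning. A dose at 8 to 10 days needs a second test.

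The cost is one sentence in two places and at most one extra blood test per woman of child-bearing potential at sites using a test dose.

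Separately, and optionally, the sampling window for test-dose pharmacokinetics in footnote v could be widened to 10 days to match Section 5.2.5.1. That is a consistency edit and does nothing for pregnancy detection.

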5.2.5.2. Pharmacokinetics for Busulfan Dose Adjustments

The dose of busulfan will be adjusted based upon busulfan PK in order to maintain appropriate levels for myeloablation (AUC goal of 1250 [range 1100 to 1350] $\mu\text{M}^*\text{min}$ for a q6h dosing regimen, or 5000 [range 4400 to 5400] $\mu\text{M}^*\text{min}$ for a qd dosing regimen). The dosage should be calculated on the basis of the lower of the ideal versus actual body weight. The dose may be adjusted appropriately based upon actual plasma busulfan levels observed. Clinical sites must be able to measure first and third day busulfan PK. Based on busulfan PK results for day 1 and day 3 of busulfan dosing, busulfan dose adjustments should be made for subsequent dosing. If feasible, daily busulfan PK measurement is recommended. It is recommended that the busulfan clearance rate is also calculated.

Instructions for once daily dosing: Samples for busulfan concentration should be collected at the end of the 3-hour infusion, 195 minutes after **start** of infusion, and 4, 5, 6, and 8 hours after the start of the infusion. Samples should not be drawn from the lumen used to infuse busulfan.

Instructions for q6h dosing: Samples for busulfan concentration should be collected at the end of the 2-hour infusion, 135 minutes after **start** of infusion, 150 minutes after start of infusion, and 3, 4, 5, and 6 hours after the start of the infusion. Samples should not be drawn from the lumen used to infuse busulfan.

After completion of the 4-day course of busulfan, there must be a minimum of 48 hours before drug product infusion to achieve optimal engraftment. Busulfan levels will be measured 48 and 72 hours after final dose of busulfan for retrospective confirmation of adequate wash-out.

5.2.6. Drug Product Infusion Procedures, Dose, and Administration

Pre-hydration and pre-medication of the subject are not required and should follow local procedures for bone marrow infusion at the clinical site.

Prior to administration, bb1111 is thawed at the clinical site (typically in a 37°C water bath), and the infusion of the drug product should be completed immediately after thawing and within a

maximum of 4 hours of its thawing. All procedures involving bb1111 must be performed using aseptic techniques by trained personnel.

bb1111 will be administered on Day 1 via IV infusion at the clinical site. The dose to be administered is $\geq 3.0 \times 10^6$ CD34+ cells/kg (for mobilized apheresed cells). Subjects who undergo more than 1 stem cell collection procedure (and subsequent transduction of those cells) will have more than 1 drug product lot, which should be administered in sequence, with one administered immediately after the other. Disposition of back-up cells collected and/or partial drug product manufactured under a prior version of the protocol will be made after discussion between the Investigator and Medical Monitor.

Vital signs are to be monitored concurrently during drug product infusion no less frequently than at the start, once during, and upon completion of the infusion. Infusion reactions, including anaphylaxis, will be managed according to the medical judgment of the physician overseeing the infusion.

5.3. Method of Assigning Subjects to Treatment

Seven subjects who consented and received drug product under version 5.0 (or earlier) of the protocol were retrospectively assigned to Group A, in which both drug product and back-up cells were derived from bone marrow.

In addition to the above 7 subjects, 1 subject who had consented under version 5.0 of the protocol, but had not yet been treated with drug product, was reconsented under protocol version 6.0 and participated in Group B1.

Subjects initially consented under version 6.0 of this protocol were part of Group B or C. In Group B1, both drug product and back-up cells were derived from bone marrow. In Group B2, plerixafor mobilization and apheresis were used for collection of back-up cells and exploratory manufacturing development *prior* to undergoing bone marrow harvest for drug product manufacture. At least 3 subjects were required to enroll in Group B, and at least 3 subjects in Group B2 were required for evaluation of DLT at each dose of plerixafor.

Group C was opened upon (1) confirmation of the safety and tolerability of plerixafor mobilization in Group B2, and (2) regulatory authority approval of the drug product manufacturing process with plerixafor-mobilized HSCs. In Group C, both drug product and back-up cells are derived from HSCs collected by plerixafor-mobilized apheresis.

Subjects in Group B2 who tolerated and successfully mobilized with plerixafor for back-up cells, and who had not yet had drug product manufactured with bone marrow harvest, were given the option to delay collection of cells for drug product manufacture until Group C opened, and they could undergo drug product manufacture from cells obtained by a subsequent cycle of plerixafor mobilization.

Subjects in Group C will undergo mobilization with plerixafor and apheresis for both manufacture of drug product and back-up cells. Group C subjects for whom adequate HSCs are collected to achieve the minimum cell dose but not for rescue, and who are not able to tolerate further plerixafor or did not mobilize well with plerixafor may be offered the option of bone marrow harvest for collection of back-up cells only, provided that drug product manufactured from mobilized cells has met criteria for dispositioning for clinical use.

5.4. Blinding, Packaging and Labeling

5.4.1. Blinding and Breaking the Blind

This is an unblinded, open-label study.

5.4.2. Packaging and Labeling

bb1111 consists of an autologous CD34+ cell-enriched population from patients with SCD that contains HSCs transduced with BB305 LVV encoding the β^{A-T87Q} -globin gene, suspended in cryopreservation solution in the final infusion bag.

The drug product will be labeled by the transduction facility according to Good Manufacturing Practices. Refer to [Section 5.7](#) for additional details regarding product accountability.

